## **10. SUBJECT DISCONTINUATION**

The removal of a study subject by the Principal Investigator could occur due to the following reasons:

- 1. Adverse Event
- 2. Concomitant treatments or illnesses incompatible with the study

- 3. Withdrawal of consent by the participant
  - a. All subjects will be informed of the fact that they may, of their own free will, withdraw their consent to participate in the study, if they so wish.
- 4. Loss of follow-up
- 5. Emergence of a non-inclusion criterion
- 6. Researchers' decision
- 7. Protocol violation

Those subjects who, for some reason, are discontinued from the study will not be replaced. Data from these subjects will not be analyzed unless the reason for their discontinuation was related to the investigational product. The Investigator should carefully track and document all premature discontinuations and their reasons on study documentation and also, when necessary, on the "adverse event" form, as well as on the study documentation.

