## 2. OBJECTIVE

The objectives of this study are to determine by repetitive epidermal contact, the primary or cumulative irritation and the allergic contact sensitization potential of the ColActive Plus Collagen Matrix Dressing, under maximized conditions, with controlled product quantity and application site. The data will be used as part of a regulatory submission to the FDA.

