# 6. SUBJECT SELECTION CRITERIA

Approximately 75 healthy subjects satisfying all criteria listed below will be enrolled to complete the study with a minimum of 50 subjects.

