# 6.2 Exclusion Criteria

Individuals meeting any of the following criteria will be excluded from study participation.

- 1. Individuals who are currently taking any medications (topical or systemic) that may mask or interfere with the test results (specifically, corticosteroids, topical and/or systemic [except nasal steroids], non steroidal anti-inflammatory drugs [e.g. ibuprofen, Advil, Motrin, aspirin > 325mg/day], antihistamines, and topical/oral immunosuppressive medications). Subjects must refrain from using any topical/oral anti-inflammatory medications during the length of the study (6 weeks).
- 2. Individuals who have a history of any acute or chronic disease that might interfere with or increase the risk on study participation. (e.g., systemic lupus erythematosus, rheumatoid arthritis, HIV positive).
- 3. Individuals who are diagnosed with chronic skin allergies (atopic dermatitis/eczema) or recently treated skin cancer within the last 12 months.
- 4. Individuals who have damaged skin in close proximity to test sites (e.g., sunburn, uneven skin pigmentation, tattoos, scars, excessive hair, active acne papules or other disfigurations).
- 5. Individuals who control their diabetes using insulin.
- 6. Individuals with any history, which in the Investigator's opinion, indicates the potential for harm to the subject or places the validity of the study in jeopardy.
- 7. Female volunteers who indicate that they are pregnant or are planning to become pregnant or nursing.
- 8. Individuals with a known history of hypersensitivity to any cosmetics, personal care products, fragrances, and/or adhesives.
- 9. Employees of ALS.

10. Individuals with a known fish allergy.

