#### 9.4 Test Product Preparation

Test Product Preparation will be performed as noted below unless otherwise requested by Sponsor. Prepare ColActive Plus Collagen Matrix Dressing samples using the following method:

Step 1: ColActive Plus Collagen Matrix Dressing: cut with sterile scissors to fit the chamber of the patch (25-millimeter diameter).
Step 2: Place the test article directly on the Hill Top Chamber®.
Step 3: 0.8mL of distilled water will be dispensed to saturate the test product.\*

Step 4: Place a Hill Top Chamber® on the test site.

\*Visual inspection will be done to confirm the entire test article has come in contact with distilled water and test product has transformed into a gel.

9.5 Test Sites/ Procedure:

The patches will be applied directly to the skin of the intrascapular regions of the back, to the right and/or left of the midline, and/or upper arms.

Subjects will be given a Panelist Instructions for the Safety Patch Test. Subjects will be dismissed with instructions to keep the test area dry while the patches are in place and to not expose the test area to direct sunlight. Subjects will be instructed to notify clinical staff during the course of the study should they begin using any new medications, cease taking any medications or have any change in their medical condition.

Patches will remain in place for a minimum of 48 hours. Subjects will be instructed to not remove the patches prior to their next scheduled visit. Subjects patched on Friday will have patches remain on until the following Monday (72 hours). The procedure will be repeated until a series of 9 consecutive 48-hour exposures have been made over 3 consecutive weeks. This is considered the induction phase.

Before each re-application, the test sites will be visually evaluated for any reaction.

Following the induction phase, subject will be given a minimum of 10-day rest period.

A challenge or test dose will be applied once to a previously unexposed test site. Clinical staff will remove the patches 48 hours post-application. Reactions will be scored 30 minutes post-removal, 24-hours post-removal, and 48-hours post-removal. The skin grader will be blinded to the treatment assignments and any previous scores.

Skin response to the test product will be evaluated according to the Berger and Bowman Scale (Section 8. Experimental Techniques and Methods).

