# **14. DATA REPORTING**

Skin responses to the test product for each subject will be presented in a table in the final report. Product reporting for skin irritation will be based on scores after the first 48hour patch removal. Product reporting for skin sensitization (contact allergy) will be based on scores after the 72hour patch removal of challenge phase.

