# **APPENDIX II:**

23-401 A	QUESTIONNAIRE	FOR SUBJECT	ENROLLMENT
23-401 A	QUESTIONNAINE	FUR SUBJECT	LINNULLINILINI

Subject ID: Subject Initials:				
1)	Are you aware that	at this study involve	s research?	YES / NO (circle one)
2)	How long is your	study participation?	,	
3)	3) For the first 9 patching visits, where will the patches containing test product be applied?			
4)	For the visit 11, w	where will the patche	es containing test product	be applied?
5)	Female volunteer	s:		
Ar	e you pregnant, or	nursing or planning	to get pregnant? YES	/ NO / MALE (circle one)
If o	of child bearing pot			ees to use while participating on study.
6)	What are some po		s expected from this study	v?
7)	How many total w	visits will you make	to the facility?	
8)	What is the expec	ted duration of the t	esting visits?	_
9)	-	-	r for the required visit dat ad open hours listed?	es and the open patch hours. Are YES / NO (circle one)
10	) Do you understan	d that you will be di	scontinued from the stud	y without full compensation if you
	fail to complete a	ll required study vis	its?	YES / NO (circle one)
11)			and emails are a courtes king the required visits li	y and not a requirement of the sted on the calendar?
				YES / NO (circle one)
12)	) Have all your que	estions about the stud	dy process been answered	? YES / NO (circle one)
	L:	b*	Fitzpatrick Score	:(I-V)
AI	_S Staff Initial	Date	Subject Init	tial Date

ALS Staff Initial

Subject Initial

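### Section 10 keeps complete first-patch irritation scores out of the analysis when a subject later stops for a reason unrelated to the product

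*Protocol*

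**What the plan says.** Section 10 sets one rule for everyone who stops early: "Data from these subjects will not be analyzed unless the reason for their discontinuation was related to the investigational product". It makes no distinction by outcome or by time of stopping. The same section adds: "Those subjects who, for some reason, are discontinued from the study will not be replaced". Its list of reasons includes withdrawn consent, loss to follow-up, the researchers' decision and protocol violation.

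Section 2 makes both irritation and sensitization objectives: "the primary or cumulative irritation and the allergic contact sensitization potential". Section 14 ties them to different times. For irritation: "Product reporting for skin irritation will be based on scores after the first 48hour patch removal". Sensitization is reported from the challenge phase.

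Section 9.5 describes the induction phase: "The procedure will be repeated until a series of 9 consecutive 48-hour exposures have been made over 3 consecutive weeks". Sites are inspected before every re-application. A rest of at least 10 days and the challenge follow.

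Section 6 gives the numbers: "Approximately 75 healthy subjects satisfying all criteria listed below will be enrolled to complete the study with a minimum of 50 subjects".

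**The concern.** The exclusion rule suits an outcome that needs the whole course, such as the challenge reading. Irritation under Section 14 is different: it is complete after one patch. Applied to both, the rule has two effects.

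- **Precision.** First-patch scores already in hand drop out of the irritation summary, and no replacement subjects are enrolled.
- **Selection.** Whether a discontinued subject counts depends on a judgement, made after exposure, of whether the stop was related to the product. Section 10 gives no cut-point for that judgement, while Section 11 grades the relationship of adverse events in six categories. Product-related stops stay in and the others go out. If the others are non-reactors, the reactor proportion rises. If a reactor's exit is recorded as unrelated, for example as withdrawn consent, it falls.

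Unrelated exits are foreseen. Besides the list in Section 10, Appendix II item 10 has subjects acknowledge that missing required visits leads to discontinuation, and Section 9.3 drops subjects who react to the water control. The data are intended for an FDA submission (Section 2).

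**Working it through.** **1. Is the score complete before the exit?** Section 14 uses the first 48-hour removal, about day 2. Section 9.5 has the site read before patch 2, so the score exists with eight patches, the rest and the challenge still to come. On the six weeks named in Section 6.2, the time remaining is (42 − 2)/42 = 95%. On the minimum schedule (21 days induction + 10 rest + 4 challenge = 35), it is (35 − 2)/35 = 94%. No section exempts irritation from the Section 10 rule.

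**2. The plan's own figures.** About 75 are enrolled and at least 50 are to complete. The tolerated loss is 75 − 50 = 25, or 25/75 = 33.3%; conversely 50/(1 − 1/3) = 75. This rate is implied, not stated. The protocol gives no power, reaction rate, dropout rate or confidence limit to reproduce.

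**3. Precision (illustration).** With zero reactors among n subjects, the exact one-sided 95% upper bound is 1 − 0.05^(1/n).

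| Unrelated losses after the first score | n analysed | Upper bound |
|---|---|---|
| 0 | 75 | 3.9% |
| 5 | 70 | 4.2% |
| 25 (outer limit) | 50 | 5.8% |

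The last row needs the whole margin to be used, every loss to be unrelated, and every loss to fall after the first score. If half of the 25 came before that score, about 62 scores would exist (75 − 12.5, rounded down), and the comparison would be 4.7% at n = 62 against 5.8% at n = 50.

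**4. Bias (illustration).** Suppose 3 of 75 subjects react at the first patch: 3/75 = 4.0%.

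- Five non-reactors leave: 3/70 = 4.3%, a factor of 75/70 = 1.07.
- Twenty-five non-reactors leave: 3/50 = 6.0%, a factor of 75/50 = 1.5.
- Five leave and one of them is a reactor whose exit is recorded as unrelated: 2/70 = 2.9%.

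The shift can go either way, and its size depends on how many leave and who they are.

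**The case against.** The strongest reply is that little is hidden. Section 10 bars analysis, not retention. Section 15 keeps raw data for at least six years, and Section 14 tabulates responses for each subject without excluding those who stopped. Section 9.5 has the sponsor told within 1–2 business days of erythema of 2 or more, or of papules, vesicles, bullae or spreading. Section 11 has all adverse events reported, related or not. All of this stands. A reader might infer that the scores are lost, or that notable reactions could be concealed; the documents support neither. What remains is that a listing is not an analysis, and the Section 14 table does not lift the Section 10 bar.

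Second, the more mechanical bias is conservative: removing non-reactors while keeping product-related stops works against the product. That is fair, and an exit that follows a strong reaction would naturally be recorded as product-related. A reader should not infer a systematic bias in the product's favour. The downward route is possible, but nothing in the protocol says how likely it is.

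Third, the protocol plans no rate or confidence limit, so the figures above are the review's own, and the 25-loss row is an extreme. This also stands, which is why they are labelled illustrations.

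Fourth, some exclusions are sensible. A reaction to the water control, an interfering medication or a violation at or before the first score can compromise that score. The fix therefore keeps such subjects out of the main summary.

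A reply that the statistical analysis plan could settle the matter does not help. The protocol sets the rule explicitly, and a plan that analysed these scores would contradict it.

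**Conclusion.** The conflict between Sections 10 and 14 holds with high confidence as a matter of text. Followed as written, the plan excludes complete first-patch irritation results from analysis and lets inclusion turn on a post-exposure judgement.

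The consequence is less certain, because actual attrition is unknown. With 5 unrelated losses the effect is modest; the 25-loss figures are an outer limit, not a forecast.

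A reader might extend the point to sensitization or to cumulative irritation. The documents do not support that. A subject who never reaches the challenge has no sensitization result, and one who leaves early has no full cumulative record. The point is confined to the first-patch result. Severity is minor to moderate.

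**What to change.** Add an exception to Section 10, for example:

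> The first-patch irritation result of Section 14 is analysed in all subjects with a valid score at the first 48-hour patch removal, whatever the reason for any later discontinuation (for withdrawn consent, as far as the consent permits use of data already collected). Subjects with a negative-control reaction, interfering medication or a protocol violation at or before that score are summarised separately, and a sensitivity summary includes them. All discontinued subjects are listed with their available scores, exposures completed and reason for stopping.

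Leave the rule for sensitization as it is, including the retention of product-related discontinuations. First-patch inclusion then no longer rests on relatedness, so no cut-point is needed for it.

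The cost is one amendment with IRB submission (Section 12) and one added summary. No new data are collected, and no visit, dose or clinical rule changes.

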## **11. ADVERSE EVENTS**

The most commonly observed reactions in this study are:

1. Itching, redness, rash, peeling, swelling and in rare cases blistering.

2. There is also a possibility of getting a reaction from the tape possible resulting in hyperpigmentation.

There also may be risks and discomforts, which are not yet known.

An adverse event (AE) is any unfavorable medical occurrence experienced by the subject, whether or not the event may be related to the test article.

Each adverse event must be promptly recorded and sufficiently documented by the Study Director in the source documentation and case report form even if the adverse event is assessed by the Study Director as unlikely to be related to the study. Adverse events are graded on a scale of severity (mild, moderate, severe, or lift threatening) and on a scale of relationship to the product (unknown, unrelated, unlikely, possible, probable, or definite). All adverse events will be reported to the Sponsor within five business days. All adverse events will be followed up until resolved, stabilized, the subject is lost to follow-up or the event is otherwise explained. All follow-up information should be reported to the Sponsor.

A serious adverse event (SAE) as defined in the CFR 312.32 is "any experience that is fatal or life threatening, is permanently disabling, requires inpatient hospitalization, or is a congenital anomaly, cancer, or overdose". All serious adverse events will be reported to the Sponsor within 24 hours of ALS Beauty & Personal Care notification.

If, according to the Investigator, medical care is warranted, appropriate referrals will be made. ALS Beauty & Personal Care will follow adverse events until resolution.

#### **12. PROTOCOL AMENDMENT**

Any changes to the study protocol will be approved in writing by the client and ALS then submitted to the IRB for approval prior to implementation in the study, unless immediate change is necessary to eliminate hazard to the subject(s). Any violations in the study conduct will be documented as protocol deviations. Protocol amendments will be signed by the Investigator and Sponsor representative.

#### **13. STUDY REPORT**

A final report will be issued to the sponsor within 4 weeks of study completion.

# **14. DATA REPORTING**

Skin responses to the test product for each subject will be presented in a table in the final report. Product reporting for skin irritation will be based on scores after the first 48hour patch removal. Product reporting for skin sensitization (contact allergy) will be based on scores after the 72hour patch removal of challenge phase.

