# 4. BACKGROUND 

Allergic contact dermatitis (sensitization) results when a substance contacting the skin has undergone an immunological alteration in its reactivity. This altered reactivity is the result of prior exposure of the material to the skin, which may lead to the hallmark visual symptoms of erythema, edema, papules.

Primary (acute) irritation is a complex biologic syndrome, with a diverse pathophysiology, natural history and clinical appearance. When exposure is sufficient and the offending agent/test material is potent, classic symptoms of acute skin irritation are seen which include hallmark visual symptoms of erythema, edema, and papules. The irritant reaction quickly peaks and then begins to heal upon removal of irritant. The onset is acute and often after one single exposure. Predictive testing is widely performed to determine the irritant potential of test agents.

This procedure is used as a predictive test for contact sensitization in humans. The procedure involves the application of a discontinuous series of occlusive patches to human skin over a three-week induction period. Induction is followed by an approximate two-week rest period. Challenge consists of a single application to naive skin.

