## Letter Grades (always upper case)

- A = Slight glazed appearance
- B = Marked glazing
- C = Glazing with peeling and cracking
- F = Glazing with fissures
- G = Film of dried serous exudate covering all or a portion of the patch site
- H = Small petechial erosions and/or scabs

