## Positive Control:

0.5% sodium lauryl sulfate (Sigma Chemicals, St. Louis, Missouri) in distilled water will be applied as a positive control. Positive control is applied on the same type of occlusive patch as the test product and is applied to the intrascapular region of the subjects' back. Positive control remains on the subjects' skin for 48 hours. The patch is removed, and the positive control site will be evaluated according to the Berger and Bowman Scale by a trained ALS staff member. Positive reactions are notated and reported in final report. Positive Control will only be applied for Induction 1.

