#### Negative Control:

Distilled water will be applied as a negative control. Negative control is applied on the same type of occlusive patch as the test product and is applied intrascapular regions of the subjects' back. Negative control remains on the subject skin for 48-72 hours. The patch is removed and will be evaluated according to Berger and Bowman Scale by a trained ALS staff member. Positive reactions are notated and reported in final report. Subjects who observe a positive reaction are dropped from the study. The negative control will be applied throughout the entire study along with test product.

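### The irritation result rests on the first patch alone, so the cumulative-irritation part of the objective has no reporting rule

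*Protocol*

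**What the plan says.** Section 2 (Objective) states that the study is to "determine by repetitive epidermal contact, the primary or cumulative irritation and the allergic contact sensitization potential" of the dressing, and that the data will support a submission to the FDA.

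Section 9.5 (Test Sites/Procedure) schedules nine induction exposures over three weeks. On readings it says: "Before each re-application, the test sites will be visually evaluated for any reaction". Section 8 scores induction on the Berger and Bowman scale, 0 to 7 with added letter grades.

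Section 14 (Data Reporting) first promises a table of each subject's skin responses, then fixes the basis of the irritation result: "Product reporting for skin irritation will be based on scores after the first 48hour patch removal".

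On the controls, section 9.3 says "Positive Control will only be applied for Induction 1" and "The negative control will be applied throughout the entire study along with test product". Section 4 (Background) says of primary irritation: "The onset is acute and often after one single exposure". It describes the overall method this way: "This procedure is used as a predictive test for contact sensitization in humans".

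**The concern.** The objective names cumulative irritation and ties the assessment to repeated contact. The reporting rule stops at the reading taken when the first patch comes off, before any repeat contact. A product with clean first-patch scores and reactions at later patches would show no reaction in its stated irritation result, under an objective that mentions cumulative irritation.

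This is not a detail that a statistical analysis plan could simply supply. The protocol does not leave the basis of the irritation result open; it sets it at the first patch. An analysis plan that added a cumulative result would go beyond that rule, and sections 2 and 14 would still not match.

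**Working it through.** The plan gives no figure to reproduce here. The check compares the objective, the schedule and the reporting rule, then counts what the rule uses.

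**Inputs.** Nine exposures, nominally 48 hours each, with Friday patches left on 72 hours (section 9.5); a reading before each re-application (section 9.5); at least 50 completing subjects and about 75 enrolled (section 6); result based on the first patch (section 14).

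**Repeat contacts behind a reading.** The reading after patch k follows k − 1 repeat contacts. For the reading that section 14 uses, k = 1, so there are 1 − 1 = 0. After the ninth patch there would be 9 − 1 = 8.

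**Readings per subject.** Nine exposures involve 9 − 1 = 8 re-applications, so 8 readings are explicit. A ninth, after the last patch, is implied but not stated. Appendix II counts nine patching visits and asks where patches go at visit 11, apparently the challenge. That suggests a visit 10 at which the ninth reading could be taken, an inference to confirm.

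**Share used by the rule.**
- Exposures: 1/9 = 11.1%.
- Explicit readings: 1/8 = 12.5%.
- Wear time, all patches 48 hours: 9 × 48 = 432 h; 48/432 = 11.1%.
- Wear time, assuming three of the nine are Friday patches: 6 × 48 + 3 × 72 = 504 h; 48/504 = 9.5%.

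**Test-product readings outside the result** (upper limits, since discontinued sites give fewer).
- 50 subjects: 50 × 8 − 50 = 350 of 400 explicit readings; with a ninth reading, 50 × 9 − 50 = 400 of 450.
- 75 subjects: 75 × 8 − 75 = 525 of 600; with a ninth reading, 75 × 9 − 75 = 600 of 675.

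All these figures restate one patch of nine. They measure how much of the induction the rule covers, not bias.

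**Where the later readings do have a role.** They would probably be listed in the section 14 table, which is not limited to the first patch. They trigger Sponsor notification, and a change or discontinuation of the test site, under section 9.5. No section gives them a part in the irritation result or defines a cumulative score.

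**Which summary would show accumulation.** Take two invented score patterns over nine readings: A scores 1 every time, and B scores 1 once, at a later patch, and 0 otherwise. The highest score is 1 for both, and neither reaches 2. The totals are 9 × 1 = 9 and 1; the means are 9/9 = 1 and 1/9 = 0.11. A peak or a count of scores of 2 or more cannot separate them; a total or mean can.

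**Control arm of such a summary.** Section 9.3 drops subjects with a positive reaction to the negative control. Section 10 leaves discontinued subjects' data out of the analysis unless the cause was product-related. Together these rules would remove the control reactors and pull the control scores towards zero.

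**Low scores.** Section 8 keeps questionable reactions (minimal, barely perceptible, or under 25% of the site) out of calculations, yet induction grade 1 is itself defined as minimal and barely perceptible. Whether grade 1 counts in an induction summary is therefore unclear.

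**The case against.** The strongest defence is that section 2 joins primary and cumulative irritation with *or*, so primary alone would satisfy it. Section 4 describes only primary irritation and presents the repeated patches as a sensitization test. The positive control runs only at Induction 1, so the first reading is the only one with a concurrent positive control. On that reading section 14 is coherent and the fault is loose wording in the objective. Repeated contact also serves sensitization, so the phrase is not without purpose.

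Much of this stands. It gives a sound reason for using the first patch for primary irritation, and it makes narrowing the objective a legitimate repair. It does not supply a rule for the cumulative irritation that section 2 names.

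It is also fair that later reactions are not hidden: they would probably be tabulated, and they are notified if they meet the criteria. Section 14 states its basis openly, so whether a reader would be misled is conjecture. The choice among total, mean or peak could properly sit in an analysis plan; the mismatch between objective and fixed basis could not.

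A reader might infer more: that the data from patches 2 to 9 are lost, that the irritation result is biased, or that a known share of reactions will be missed. The documents do not support any of these. The scores are collected, the first-patch result is valid for what it measures, and no late-reaction rate is given from which to derive a number.

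**Conclusion.** The point holds as a mismatch between objective and reporting rule. The first-patch score can support a primary-irritation result only. Readings after patches 2 to 9, 8 of the 9 exposures, do not enter the stated irritation result. This follows from the text and needs no assumed reaction rate. It does assume that no other rule, outside the protocol at hand, widens the section 14 basis; even then the protocol's own sections would need aligning.

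Severity is minor to moderate. The individual scores are probably still tabulated, which limits the harm. The intended regulatory use is the reason to settle the wording.

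**What to change.** Reconcile sections 2 and 14 in one of two ways.

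**Option 1: report both components.** Keep the first-patch score for primary irritation. Add to section 14 a descriptive cumulative summary over all induction readings, for test product and negative control:
- State a reading after removal of the ninth patch.
- Give the per-subject total (or mean) of numeric Berger and Bowman scores, combining original and any new site. Show the highest score and the number of subjects scoring 2 or more alongside, and list letter grades separately.
- State how readings missing after a site change or discontinuation for a reaction are scored; for example, carry the last score forward and count the subject as a reactor.
- For subjects dropped for a negative-control reaction, include the readings obtained up to and including the one that led to removal, as an exception to section 10 for this summary.
- State whether the section 8 exclusion of minimal or barely perceptible reactions applies to induction grade 1.
- Note that there is no concurrent positive control after Induction 1.

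**Option 2: narrow the objective.** Limit the irritation objective in section 2 to primary irritation and make no cumulative-irritation claim.

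Either option needs one amendment under section 12, with written approval from the client and the testing facility and then IRB approval. Option 1 adds one table; eight of its nine readings are already required, and the negative control already runs throughout. Option 2 changes wording only but gives up the cumulative claim.
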